## 5. PARTICIPANT MANAGEMENT

## 5.1 Overview

Study treatment interventions are described above (Section 3.4). They will be provided free of charge to BetaFat participants. HbA1c will be monitored every 6 months. Procedures to be followed for rising HbA1c levels are described in Section 7.4.4. Beyond the treatment of the glucose-aspect of pre-diabetes and diabetes care, the research study will not assume responsibility for the medical care of the participant. Non-glucose aspects of diabetes care (e.g., blood pressure, lipids) and non-diabetes related medical problems will be referred to the participant's primary care provider. When a potential treatment could affect the study's outcome(s), the study's physician will discuss the choices with the participant's primary care provider. When a potential treatment could affect the Study labs will be shared with the provider, with the participant's primary care provider. For those participants who do not have a primary care provider, the study staff will help find appropriate medical care.

## 5.2 Drug Distribution

Metformin will be obtained from the same distributor used by other studies in the RISE consortium. The local research pharmacy of the USC Clinical Research Organization (CRO) will organize and maintain inventory. *Sufficient* medication is kept on hand to allow medication distribution for the next 3 month period. This would include medications required for the next 12 randomized enrollees (i.e., on average 3 initial distributions for each of the 4 treatment arms) plus all of the upcoming distributions to enrolled participants who will be returning within 3 months. Expiration dates of all medications will be double checked and documented

on arrival at the CRO pharmacy and at the time of distribution to participants to ensure that the provided supplies will not expire during the current treatment interval.

#### 5.3 Adherence Measures

Adherence is documented, monitored, and addressed as part of participant care and management and to monitor whether procedures are being implemented and followed. Adherence refers to all study procedures – not only taking the prescribed amount of study drug, but also attending scheduled study visits and completing procedures at those visits. The goal is to maintain high levels of adherence in all participants. Primary adherence measures will address visit attendance and completion of study procedures and medication adherence. Participants will be instructed to bring all study medication (including empty bottles) to study visits for assessment of medication compliance.

#### 5.4 Retention

Retention refers to efforts to prevent participant dropout or withdrawal from the study. It is critically important to successfully engage and retain participation over the course of the trial. For purposes of sample size estimation, investigators have predicted an annual withdrawal rate of 10% during the 24-month treatment periods and have adjusted sample size to meet study requirements. However, lower rates of attrition are desirable.

The Study Coordinator at each site is primarily responsible for monitoring participant attrition and initiating team conferences for retention strategies or dropout recovery rates. Subjects missing scheduled visits will be contacted within 24 hours of the scheduled visit to reschedule and discuss strategies to improve compliance. If the subject can't be contacted, a certified letter will be sent to encourage continuation in the trial even if they no longer wish to take the study medication. Study staff may implement additional efforts to personalize the study.

Attrition is monitored regularly by the Data Center and the RISE Consortium Recruitment and Retention Committee. An attempt is made to collect data on the reason for leaving the study in the case of a participant who withdraws. Studies in the RISE Consortium are encouraged to share their ideas and experiences via regular communication and conference calls for Study Coordinators. The BetaFat Data Center will prepare monthly reports on visit completion, compliance with the BetaFat Study protocol and participants on inactive follow-up.

Potential participants will be provided introductory material that will emphasize the importance of completing the study regardless of treatment assignment. We will emphasize this importance during the screening, enrollment and baseline testing procedures. Should dropout rates exceed the projected 10% per year, we will explore several options: (a) we may

intensify messaging about the importance of participation and identify reasons for drop-outs, targeting them for retention efforts; (b) we may increase overall enrollment if the difference between real and projected drop-outs is small (budgets limit large increases in enrollment); (c) we will examine projected completion in relation to power, noting that our current 80% power threshold is below the projected effect size, so that we may be able to tolerate some excess loss to follow-up; (d) if dropouts are occurring after 12 months, we may consider changing the primary outcomes to rates of change in the two primary beta cell measures, as we have used in prior observational studies with different durations of follow-up. Note that we plan to assess main outcomes at 12 and 24 months on treatment, allowing this approach.

# **6 DATA COLLECTION**

## 6.1 Pre-screening and Screening Eligibility Measurements

*Prescreening*: Prescreening for potential eligibility is done using clinical databases at Kaiser Permanente Southern California and the Ambulatory Care Network of Los Angeles County. Participants are eligible to continue screening procedures if they have an A1C within six months that was 5.8-7.0% and are 20-65 years old with BMI 30-40 kg/m2. For Kaiser, letters are sent to potential participants describing the purpose of the study and providing individuals the opportunity to opt in to be contacted. For the ACN, potential participants are contacted directly. In both cases, a study recruiter interviews potential subjects by phone to determine potential eligibility and interest in the study.

*Screening*: Participants who meet pre-screening eligibility criteria are invited to the USC Clinical Trials Unit to provide informed consent and complete screening, including a directed history and physical exam, clinical laboratory tests, and a 2-hr, 75 g OGTT.

Table 6.1: Data Collection during Screening							
STEP	TEST / PROCEDURE	COMMENTS					
1) Pre-screening	HbA1C, BMI (EHR), age, ICD-9 codes	Contact if A1C 5.8-7.0%, age 20- 65, BMI 30-40 kg/m 					
	Phone Screening questionnaire	Initial review of eligibility					
2) Screening	fasting and 2-hr glucose (75 gram OGTT; measured at central lab), A1C	Eligibility: fasting glucose >90 mg/dl; 2-h glucose ≥140 mg/dl, AIC <7.0%					
	Clinical eligibility labs (local clinical lab)* Targeted history and physical exam, Beck Depression Inventory	Laboratory eligibility criteria Eligibility evaluation					

# 6.2 Main Study Procedures

The timing of major study procedures is illustrated in the Figure 3, Section 3 above. Data to determine main study outcomes using hyperglycemic clamp procedures will be obtained at baseline and study end, which will be defined as either the end of 24 months after initiation of metformin or placement of gastric band, or at the time of treatment failure (A1C >8.0% on two successive visits). Data for secondary analyses will be determined at other study visits. Blood and urine samples will be collected for planned measures and extra blood and urine samples will be stored for future analyses. Further details on these measures are provided below, and are summarized in Table 6.2.

	Baseline	2-mo	4-mo	6-mo	8-mo	10-mo	12-mo	15-mo	18-mo	21-mo	24 mo
Exam	X	X	Х	Х	Х	Х	Х	Х	X	Х	Х
OGTT	X						Х				Х
Hyperglycic Clamp	X						Х				Х
DEXA	X						Х				Х
MRI	X						Х				Х
A1C	X		Х	Х		Х	X		X		Х
Fasting/Biomarkers	X			Х			Х		X		Х
Band Questionnaires	X			Х			Х		X		Х
Sleep Questionnaires	X										
Clinical Labs-1	X			Х			Х		X		Х
Clinical Labs-2				Х			Х		X		Х

## 6.2.1 Fasting Blood and Urine Samples (see Table 6.2)

HbA1c will be measured and fasting blood and urine samples will be collected every six months. Aliquots of fasting blood and urine will be stored for subsequent measurement of biomarkers. A blood sample for DNA will be collected at randomization. Routine chemistries will safety will be done at baseline and every 6 months.

## 6.2.2 Oral Glucose Tolerance Test (OGTT)

Participants will come to the clinical research testing facility in the morning following a 10-12 hour overnight fast. They will drink 75 grams of an oral glucose solution (centrally provided from a single manufacturer) over ≤5 minutes. Blood samples will be obtained at -10, -5, 10, 20, 30, 60, 90, 120, 150 and 180 min relative to glucose ingestion. OGTT procedures will be performed at baseline and 12 and 24 months after initiation of metformin or placement of gastric bands.

## 6.2.3 Hyperglycemic Clamp

Hyperglycemic clamps (at approximately 200 mg/dl) will be performed after a 10-12 hour overnight fast at baseline and at 12 and 24 months after initiation of metformin or placement of gastric bands. The clamp procedure will incorporate 3 main sets of blood sampling for the planned outcome measurements: first phase (0-10 minutes); second phase (100-120 minutes); and maximal stimulated responses (from 10 minutes before until 10 minutes after arginine injection once plasma glucose has been raised to~450 mg/dl). A priming glucose bolus will be used to stimulate first phase responses, a continuous dextrose infusion will be used to create steady state hyperglycemia at ~200 mg/dl for second phase and then raise glucose to ~450 mg/dl for maximum response to arginine. Arterialized venous blood samples will be obtained at 5-min intervals throughout for measurement of plasma glucose concentration to guide the glucose infusion.

For the OGTT and clamp measures, participants will be asked to refrain from vigorous exercise and tobacco use for 24 hours before the initiation of testing. Study medications will be withheld the morning of testing.

#### 6.2.4 DEXA Scans

Patients lie flat for 10 min while DEXA is performed by a licensed technician using a Hologic Discovery A scanner. Body fat is calculated using software provided by the manufacturer. Results are transferred electronically to the study database to allow analysis of fat content by regions of interest. Bone mineral density will also be determined from the DEXAs

#### 6.2.5 MRI Scans

Approximately 80 5mm axial slices are obtained from the top of the liver to the pelvis using a series of 10-15 second breath holds on USC's research dedicated GE Healthcare 3 Tesla magnet. The procedure takes approximately 30 minutes. Iterative decomposition of water and fat with echo asymmetry and least-squares estimation (IDEAL) is used to delineate subcutaneous and visceral fat depots and quantify organ fat. SliceOmatic (Tomovision, Inc.) is used for post-image processing to compute subcutaneous and visceral adipose tissue volume and fractional fat content of liver and pancreas.

## 6.2.6 Physical Measures

Height will be measured with a stadiometer. Weight will be measured with a calibrated electronic scale. Waist and hip circumferences will be measured at the mid-point between the iliac crest and the lowest rib (waist), and at the top of the femur (hip) with the participant standing upright. Body fat and regional fat distribution will be measured by DEXA. Abdominal subcutaneous and visceral fat and hepatic and pancreatic fat will be measured by magnetic resonance imaging (MRI).

## 6.2.7 Questionnaires

Participants will complete the Pittsburgh Sleep Questionnaire, Epworth Sleepiness Scale and Berlin Questionnaire at baseline for analysis of sleep-related measures as potential predictors of response to treatment. Dietary intake is assessed the Block Food Frequency Questionnaire. Quality of life is assessed using the RAND SF-36. Bariatric Analysis and Reporting Outcomes System (BAROS) is used to assess clinical outcomes related to gastric band patients. Visual Analog Scale is used to assess pain.

## 6.2.8 Safety Measures

Clinical labs for safety monitoring (local lab), including CBC, serum transaminase levels and creatinine, will be collected at baseline and every 6 months during treatment for all study participants. Additional measurements of vitamins B1, B6, B12; 1.25OH vitamin D; and ferritin will be made every six months during treatment for participants on the LAP-Band arm of the trial. Abnormal laboratory values that, in the estimation of the BetaFat clinician investigators, require medical attention will be provided to participants, who will be advised to follow-up the abnormal value(s) with his or her primary care provider. Additionally, the BetaFat team will communicate the abnormal laboratory value(s) directly to the primary provider. Adverse events (AE) will be surveyed at each visit using a standardized questionnaire. Pregnancy tests (local lab) will be performed in women with child-bearing potential before each DEXA scan and if indicated by symptoms and menstrual history prior to other study procedures.

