## 3.4.2 Gastric Band Arm

The LapBand will be placed and participants will be followed according to standard clinical practice under the supervision of [name]. Costs for these procedures will be paid by Allergan in the form of an unrestricted research grant. Pre-operative evaluation will include a psychological evaluation, a cardiac evaluation with EKG and stress testing, evaluation by an anesthesiologist, a chest X-ray and clinical lab testing (CBC, chemistries, UA, PT/PTT, hepatitis panel and, for women, pregnancy test). Participants also meet with the bariatric nutritionist for education on dietary restrictions that will apply once the band is in place.

Surgeries for placement of LapBands will be performed by [name] at the Keck Hospital of USC. The procedure is done laparoscopically on outpatients. Patients see [name] 2 weeks after surgery for wound check and suture removal. Band adjustments are performed by [name], members of his bariatric surgical team, and/or [name]. Adjustments will commence ~4 weeks after surgery and will recur every 1-3 months at the time of regular research visits. Adjustments will be made based on specific criteria consisting of symptoms of satiety and hunger, dietary history, and weight loss. Patients will revert to liquid diet for 24-48 hours after band adjustments and advance diet over the next 3-5 days. The bariatric team has an on-call system to evaluate and treat patients who have symptoms related to their bands. Post-operative laboratory assessments include CBC; chemistries; vitamin B1, B6 and B12 levels; ferritin; and 25(OH) vitamin D (see Table 2 for testing schedule).

Although both groups will be on active treatment, it is possible that glycemic control could deteriorate to a point of needing additional therapies. We will be monitoring HbA1C at six month intervals. If a value is >8.0%, we will repeat it in one month and, if it remains >8.0% we

will consider the subject to have reached a safety endpoint for the trial. We will perform end-of study visits (scheduled for 24 months in Table 3) and refer the subject for care of his/her diabetes.

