# 8.3 Reporting Adverse Events

AEs will be ascertained in an unbiased manner using standard questions that are identical and administered identically to participants in both treatment arms. To accomplish this, AEs will be reported on a standard form that is completed by the study staff at each regular study visit. Targeted non-serious AEs (e.g., abdominal pain) are ascertained by asking questions relating to

specific events of import in prediabetic or diabetic participants as well as side effects that may be associated with any of the study treatment arms. AEs also include any significantly abnormal physical finding identified on examination and any significantly abnormal laboratory result obtained on the patient between visits or at the time of the visit.

In order to facilitate timely reporting of SAEs, the clinical center staff who learn of an SAE must enter the completed RISE Consortium Serious Adverse Event Report prior to the close of the following business day.

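### Vitamin and ferritin labs are scheduled only in the band arm and only after surgery, so low values have no scheduled pre-surgery comparator and by-arm lab AE counts would partly reflect who was tested

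*Combined protocol and SAP*

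**What the plan says.** All references are to the combined protocol and SAP.

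- **Shared safety labs (section 6.2.8).** CBC, transaminases and creatinine "will be collected at baseline and every 6 months during treatment for all study participants".
- **Nutritional panel (section 6.2.8).** The next sentence says that further measurements of "vitamins B1, B6, B12; 1.25OH vitamin D; and ferritin will be made every six months during treatment for participants on the LAP-Band arm". It mentions neither a baseline draw nor the metformin arm.
- **Band arm work-up (section 3.4.2).** The pre-operative evaluation includes "clinical lab testing (CBC, chemistries, UA, PT/PTT, hepatitis panel and, for women, pregnancy test", with none of the five nutritional analytes. They appear only in the post-operative list, as "vitamin B1, B6 and B12 levels; ferritin; and 25(OH) vitamin D".
- **Schedule table (section 6.2).** The row "Clinical Labs-2" is marked at 6, 12, 18 and 24 months and not at baseline.
- **AE definition (section 8.3).** AEs include "any significantly abnormal laboratory result obtained on the patient between visits or at the time of the visit". The same section says "AEs will be ascertained in an unbiased manner using standard questions that are identical and administered identically to participants in both treatment arms".
- **Metformin and B12 (sections 7.3.1 and 7.4.1).** Reduced B12 is listed as a known metformin effect. It is monitored by following the package insert and by an annual CBC.
- **Stored samples (section 6.2.1).** "Aliquots of fasting blood and urine will be stored for subsequent measurement of biomarkers".

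**The concern.** Two things follow from testing one arm only, and only after the intervention.

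First, interpretation in the individual. If a band participant has low ferritin or B12 at month 6, the schedule offers no earlier value to show whether the deficit was there before the band. Clinicians would be deciding on care without it.

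Second, interpretation across arms. Because a significantly abnormal result is itself an AE, an analyte assayed on schedule in one arm can generate scheduled AEs only in that arm. An excess in the band column would mix real nutritional effects with the fact of having been tested. An abnormal value found off schedule would still count in either arm, so the metformin count need not be zero, but the opportunity is unequal.

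A separate textual matter is that the two descriptions of the panel name different vitamin D analytes: 25(OH) in section 3.4.2 and 1.25OH in section 6.2.8. As written, the lab could run either.

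**Working it through.** The plan states no figure on this point to reproduce, so the check is a reading of the sections against each other plus a count of scheduled assays.

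**Is there a scheduled pre-surgery value?** Section 6.2.8 gives a baseline draw to the shared labs and not to the nutritional panel. Section 3.4.2 omits the five analytes before surgery and lists them after it. The two sections agree, and they settle the question without the schedule table. The table fits: the Clinical Labs-1 row has a baseline mark and the Clinical Labs-2 row has none. However, the visible text does not define Clinical Labs-2, so matching it to the panel is an inference from timing.

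**Inputs for the count.** Five analytes (sections 3.4.2 and 6.2.8); four on-treatment visits at 6, 12, 18 and 24 months (six-monthly, over 24 months); 44 band participants and about 35 completers per group (section 9.3).

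**Scheduled results now.**
- Per band completer: 5 x 4 = 20. Per metformin completer: 0.
- Band arm, 35 completers: 20 x 35 = 700. If all 44 completed: 20 x 44 = 880. The upper figure assumes no loss, against the planned 10% per year.

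These are counts of opportunities for a flag. They do not measure bias.

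**How many flags?** The documents give neither a rate nor a threshold for a significantly abnormal result. As an assumption only, take 0.5% to 5% per test. Expected flagged results among 35 band completers would be 700 x 0.005 = 3.5 up to 700 x 0.05 = 35, against no scheduled opportunity on metformin. Repeated low values in one person might be recorded as a single AE, so AE counts could be lower. The tenfold range shows why no estimate is offered.

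**After the fix.** A band completer would have 5 + 20 = 25 scheduled results, against 0 on metformin. The pre-surgery draw supplies the comparator but leaves the between-arm difference in testing, so the labelling rule is needed as well.

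**Cost of the draw.** 44 x 5 = 220 assays at most.

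**The case against.** The strongest reply is that the panel is deliberate arm-specific care. Section 3.4.2 follows band patients under standard clinical practice, and section 7.4.1 sets its own monitoring rules for metformin. That stands: the panel is reasonable and should stay.

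Three stronger readings are tempting, and the documents do not support them.

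- *The plan breaks its own promise of equal AE ascertainment.* Section 8.3 promises identical questions, identically administered. It does not promise identical laboratory panels.
- *The trial's safety comparison is biased.* Section 9 plans no between-arm AE comparison. Section 8.4 states by-arm DSMB monitoring for serious AEs only, and the Safety Monitoring Committee reviews AEs blinded. The text does not say whether non-serious AE tables are split by arm, so the distortion is conditional on such a table being made.
- *B12 is unmonitored on metformin.* Sections 7.3.1 and 7.4.1 cover it by package-insert guidelines and CBC, and section 6.2.8 gives CBC to everyone at baseline and six-monthly. The insert is not in the documents and may call for an assay. Scheduled B12 on metformin is optional.

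There is also partial recourse for the missing baseline. Fasting aliquots are stored, ferritin is a named candidate marker (section 2.4.3), and anemia is an exclusion (section 3.5.2). But section 2.4.3 places the biomarker use of stored specimens after the main outcomes are known, which is too late for a decision at month 6.

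Finally, removing band-only laboratory AEs from by-arm tables would be the wrong remedy, because it could hide genuine harm from the device.

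**Conclusion.** The point holds at minor severity, as a cheap improvement. Five analytes are scheduled only in the band arm and only after surgery, so a low post-operative value lacks a scheduled comparator. Any by-arm count of the resulting laboratory AEs would partly reflect testing: 20 scheduled results per band completer against 0. The analyte naming conflict is plain on the text.

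The conclusion rests on sections 3.4.2, 6.2.8 and 8.3 as they stand. It assumes that no table note lost in extraction adds a baseline panel; section 3.4.2 points to a Table 2 testing schedule, and no table with that number is visible. The between-arm part matters only if laboratory AEs are shown by arm. Its size cannot be estimated from the documents. The primary outcomes and their analysis are unaffected.

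**What to change.** 1. **Pre-surgery panel.** Add B1, B6, B12, vitamin D and ferritin once to the existing pre-operative blood draw in the band arm (section 3.4.2). This is at most 220 assays with no added visit. The downside is assay cost, and section 2.4.3 notes budget limits.
2. **Labelled reporting.** In any by-arm AE table, put AEs arising only from these band-only tests on a separate line. State there that metformin participants were not scheduled for the tests, and do not interpret the line as a treatment difference. Keep the events in the report. This costs one sentence in the plan.
3. **Analyte name.** Change section 6.2.8 to 25(OH) vitamin D, to match section 3.4.2. This is a one-term correction, worth confirming with the local lab.

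The AE definition does not change. These elements appear specific to BetaFat, in which case section 11.9 requires only the local investigators and the DSMB, followed by IRB resubmission. Scheduled B12 on metformin may be added if wanted, but the fix does not depend on it.
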